5.1.1.2 Prophylaxis initiation cohort for evaluation

[figure not shown]
Patients will be eligible to enter the cohort on initiation of Takhzyro, Haegarda, or Cinryze as a prophylactic treatment during October 10, 2008 through October 3rd, 2019 (Figure 1). October 2008 was selected as the start of the study period based on the approval date for Cinryze, the earliest of the medications to be approved. Clinical experts confirmed that 2008 reflects the current treatment paradigm of medications targeting the BK pathway and that all new treatments after 2008 reflect a continual shift away from inferior anabolic androgen therapies. The study period was also selected to maximize sample size for this rare disease.

New use will be defined as no use of Takhzyro or Haegarda, during the 180 days prior (washout period), and no use of Cinryze as a prophylactic treatment during this 180-day washout period. Because Cinryze is used for both acute attacks (off label) and prophylaxis, patients will be excluded based on evidence of prophylactic use of Cinryze (see definition in Annex 2) during the 180 days prior to cohort entry and will be required to have continuous enrollment and evidence of recurring use during the 90 days following cohort entry. Patients receiving other prophylactic treatments (see Annex 1) during the baseline period will also be excluded. Each patient will be included only once, on the first qualifying event. Patients will be required to have at least 180 days of enrollment prior to cohort entry to obtain baseline attack rates.

Using this cohort, we will evaluate baseline outcomes. Patients' demographic characteristics will be assessed at cohort entry. Patients' attack rates, and attack-related medical service utilization and costs will be evaluated.

Note: HAE does not have specific ICD9/10 diagnostic codes. We used initiation of HAE specific treatment to identify patients of interest (i.e., patients with HAE). The method of using HAE treatments to identify HAE patients has been used widely in the literature (Tachdjian 2020, Banerji 2020, [Vande Walle 2018](#)).¹⁻³ In addition, there is no indication that HAE treatments are used off-label for non-HAE patients.

Figure 1: Prophylaxis initiation cohort study design diagram

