5.2.1.4 HAE attack rates

Observational studies that evaluate attack rates in claims or EHR data sets are limited. There is currently no validated method to evaluate HAE attacks in claims data.

In creating our definitions of severe and non-severe attacks, we took guidance from clinical experts, treatment guidelines, and published literature that identified symptoms ([Longhurst & Bork 2019](#))⁵ or used diagnoses codes indicative of an attack (Tachdjian 2020).¹ Symptoms and diagnoses codes were cross referenced in a de novo code search to capture both ICD-9 and ICD-10 codes.

Attacks are defined by severity:

- **Severe attack:** Treatment guidelines and empirical data suggest that severe attacks are typically treated in the ED.⁶ For this analysis, severe attack will be defined in two ways: broadly as all-cause ED visits with or without hospitalization and more specifically as HAE ED visits with or without hospitalization. HAE specific severe attacks will be defined by a claim for an ED visit with or without hospitalization that includes diagnoses and drugs indicative of an attack (see Annex 2).
- **Non-severe attack-** Non-severe attacks are treated with on-demand therapy either by self-administration or administration by a healthcare professional. An attack treated by a healthcare professional will be defined as a medical service claim for an on-demand therapy occurring outside an inpatient or ED setting (e.g., physician office). For self-administration, we will estimate the number of attacks treated by calculating the number of doses dispensed based on dispensed quantity and approved dosages. Based on [treatment guidelines](#),⁶ patients should readily have on-demand therapy to treat two attacks, thus we will consider any doses dispensed over the two on-hand dosages of on-demand therapy as evidence of an attack.

Data on the duration of attacks by severity is limited, however attacks generally last between two and five days.⁷ Thus, on-demand therapy administrations by a healthcare professional, ED visits, and inpatient hospitalizations occurring within five days of each other will be considered part of a single attack. In cases where an on-demand therapy administration occurs within five days of an ED visit or hospitalization, the attack will be counted as a severe attack.

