Android Methitest Testred Virilon (Methyltestosterone)	NDCs: 00187-0902-01 00115-1408-01 00187-0901-01 00115-7037-01	Clinical Pharmacology Database²⁰
Winstrol (Stanozolol)	NDCs: 0024-2253-04??	Clinical Pharmacology Database²⁰
Prophylactic use of Cinryze and Ruconest	Algorithm and code lists	Source
Cinryze prophylactic use	Cinryze is indicated for prophylaxis, but is used off-label for acute attacks. Prophylactic use will be defined as continuous refills of Cinryze averaging ≥ 1500 IU/week for ≥ 90 days.	Riedl 2018²²
Ruconest prophylactic use	Ruconest is indicated for on-demand use, but is used off-label for prophylaxis. Patients with Ruconest prophylactic use will be excluded from the cohort. Prophylaxis use will be defined as continuous refills of Ruconest averaging 50 IU/kg once weekly for 90 days.	Riedl 2018²²
every four-week	Used to determine if a dose reduction occurred.	

administration of Takhzyro	This will be measured over a 90-day follow-up period based on total dose <= 1200 mg over that period. The 1200 mg is based on three 300 mg injections plus one additional injection to account for potential variation in exact timing.	
Attack severity	Algorithm and code lists	Source
Severe	
ED visit with/without hospitalization, identified based on “Type of service” coded as inpatient or emergency room. Events identified as HAE-specific include at least one of the following diagnose (as a primary diagnosis for hospitalizations /or treatments indicative of an attack:
 
 € Codes often associated with HAE: ICD-9-CM 277.6 or ICD-10-CM D84.1 € Angioedema diagnosis: ICD-9-CM 995.1 or ICD-10-CM T78.3* € Administration of on-demand HAE treatment € Diagnosis of swelling, abdominal pain, or asphyxiation: 
 o ICD-9-CM 518.81, 518.84, 787.0*, 782.2, 789.0*, 786.02, 786.05, 786.1 o ICD-10-CM J96.0*, J96.2*, J96.9*, R06.0*, R06.1, R10.*, R11.*, R22.0*, R22.1, R19.0 	
UpToDate states severe attacks are treated in ED.²³
 
Tachdjian 2020¹
 
Zilberberg 2010²⁴
 
Longhurst & Bork, 2019

Non- severe attack	
Each dose of an on-demand therapy over two acute attack doses is considered an attack. The number of doses dispensed will be calculated from the quantity dispensed and recommended dose and
 
Any on-demand therapy administered outside an inpatient or emergency room setting will be considered a non-severe attack.
	
Utilization	Algorithm and code lists	Source

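### Annex 2 states no diagnosis position for ED visits, so an unrelated ED visit carrying 277.6/D84.1 as a background code can count as an HAE-specific severe attack

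*Protocol*

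**What the plan says.** Section 5.2.1.4 of the protocol defines severe attacks in two ways: "broadly as all-cause ED visits with or without hospitalization and more specifically as HAE ED visits with or without hospitalization". For the narrower version it asks for a claim "that includes diagnoses and drugs indicative of an attack (see Annex 2".

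Section 5.2 sends the reader to Annex 2 for all variable definitions. There, severe events are "identified based on “Type of service” coded as inpatient or emergency room". On the HAE-specific subset Annex 2 says: "Events identified as HAE-specific include at least one of the following diagnose (as a primary diagnosis for hospitalizations". The sentence then continues with a slash and "or treatments indicative of an attack". The parenthesis is never closed. The first item on the list is "Codes often associated with HAE: ICD-9-CM 277.6 or ICD-10-CM D84.1". Angioedema codes, on-demand treatment, and codes for swelling, abdominal pain and respiratory symptoms follow.

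On the cohort, section 5.1.1.2 says: "We used initiation of HAE specific treatment to identify patients of interest (i.e., patients with HAE".

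The sensitivity analyses on attack definitions in section 5.4.1.4 vary the five-day window and the two on-hand doses. Diagnosis position is not varied.

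**The concern.** Because one listed item is enough, 277.6/D84.1 can qualify an ED visit by itself. In a cohort made up of patients treated for HAE, that code may describe the patient's history and not the reason for the visit. For hospitalizations the protocol guards against this by requiring the primary position; for ED visits it states no guard. An ED visit for an injury or infection with D84.1 listed second would then be scored as an HAE-specific severe attack.

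The HAE-specific definition feeds several Table 2 outputs: the combined attack rate (prior base case 3.39 per month), the split by severity, the percent of severe HAE-specific attacks hospitalized (prior base case 40.9%), and HAE-specific ED utilization and cost. The study's purpose is to supply updated inputs of this kind to the cost-effectiveness model. Table 3 uses the same severe definition for follow-up, although section 5.1.1.3 says that analysis does not directly influence the model.

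**Working it through.** **The rule as written.** The protocol gives no figure to reproduce, so the check starts with the text.

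- Hospitalization: a listed diagnosis in primary position, or a listed treatment. Section 5.3.1.2 says drugs used during hospital stays are not recorded, so in practice the primary diagnosis is nearly the only route.
- ED visit: a listed diagnosis with no position stated, or a listed treatment.
- Section 5.2.1.4: diagnoses joined to drugs by 'and'. Read literally, a background code alone would not qualify. Annex 2 asks for at least one item and joins the two kinds by a slash and 'or'. The two passages conflict, and section 5.2.1.4 itself points to Annex 2.

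**Size, by assumption only.** Let v be unrelated ED visits per patient-month and q the share of them carrying 277.6/D84.1 in a secondary position. The documents give neither. Assume v = 0.02 to 0.10 and q = 25% to 75%. The false events per patient-month are f = v × q:

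- low: 0.02 × 0.25 = 0.005
- central: 0.05 × 0.50 = 0.025
- high: 0.10 × 0.75 = 0.075

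Events within five days of each other merge into one attack, so some false visits would not add an event.

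*Against the combined rate of 3.39 per month (Table 2, prior base case):* 0.005/3.39 = 0.15%; 0.025/3.39 = 0.7%; 0.075/3.39 = 2.2%.

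*Against a severe-only rate.* The documents give none; take 0.2 and 0.1 per month as assumptions.

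- central: 0.025/0.2 = 12.5%; 0.025/0.1 = 25%
- full range: from 0.005/0.2 = 2.5% to 0.075/0.1 = 75%

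*Percent hospitalized.* Let r be the false events as a fraction of true severe events, and a the share of false events that end in a counted hospitalization. With a true share of 40.9%, the observed share is (40.9% + r × a)/(1 + r).

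- a = 0 (all false events ED-only): r = 0.125 gives 40.9%/1.125 = 36.4%; r = 0.25 gives 40.9%/1.25 = 32.7%
- a = 20%: r = 0.125 gives (40.9% + 2.5%)/1.125 = 38.6%; r = 0.25 gives (40.9% + 5%)/1.25 = 36.7%
- a = 40.9%: no change

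The percent hospitalized therefore falls only if false events are admitted less often than true ones, and a = 0 is the extreme case.

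**The case against.** The strongest counter-argument is that Annex 2 does not say ED visits qualify on a code in any position. It says nothing on ED position, in a sentence whose open parenthesis leaves the reach of the qualifier unclear. Section 5.2.1.4, read literally, would exclude a lone background code. Both points stand, so any-position acceptance is an inference from silence. They do not settle the matter, because the definition that an analyst is sent to is Annex 2, and the conflict has to be resolved in any case.

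A reader might go further and infer that every ED visit in the cohort would count, so that the HAE-specific definition collapses into the all-cause one. The documents do not support that. Section 5.1.1.2 states that HAE has no specific ICD code, Annex 2 calls 277.6/D84.1 only often associated with HAE, and nothing shows how often these codes appear on unrelated visits. A reader might also infer that the combined attack rate is seriously distorted; at the assumed values it is not.

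Two safeguards are partial. The all-cause severe count is reported as well, but it gives only an upper bound. Section 5.4.1.5 discloses that no validated algorithm exists and refers to a Model Analysis Plan, which is not at hand, for how attack estimates are used; neither supplies an ED position rule.

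Finally, requiring the primary position as the only main definition would buy specificity by losing true attacks. That trade-off is a matter of judgement, and the objection is fair.

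**Conclusion.** The concern holds in limited form. Annex 2 restricts diagnosis position for hospitalizations, states no position for ED visits, and lists codes that HAE patients may carry as background. Applied as written, it allows unrelated ED visits into the HAE-specific severe count, and no planned analysis shows how many.

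The bias in the severe rate and ED utilization is upward. The bias in percent hospitalized is downward to the extent that the false events are ED-only. The effect on cost per ED visit has no direction that the documents determine. The size is unknown: every figure for it rests on assumed visit rates, coding shares and severe rates. Under those assumptions the combined rate moves by about 0.1% to 2.2%, while the severe-only outputs could move materially.

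**What to change.** 1. In Annex 2, state the ED position rule so that 277.6/D84.1 in a secondary position does not qualify an ED visit alone, but only with a listed angioedema or symptom code or on-demand treatment on the visit. Close the parenthesis so that the scope of the primary-diagnosis limit is clear.
2. In section 5.4.1.4, add a sensitivity analysis reporting the HAE-specific severe rate and percent hospitalized under both a primary-position and an any-position ED rule. This also shows the influence of symptom codes in secondary positions, which item 1 leaves in place.
3. Reconcile the 'and' in section 5.2.1.4 with the at-least-one wording and the 'or' in Annex 2.

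The cost is a few lines of text and one rerun. The stricter count may miss some true attacks whose first code is not on the list; the any-position count bounds that loss. Unrelated visits with abdominal pain or vomiting listed first would still count under either rule.

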5.4.1.3 Exploratory Follow-up descriptive analyses

Due to the small sample size, there is a lack of power to complete a formal pre/post analysis to detect a meaningful difference in attack rates. Thus, our follow-up analysis will be descriptive.

In the follow up period, we are interested in exploring the frequency of attacks after initiation of prophylaxis therapy, understanding utilization, and determining how many months patients were attack free after initiation. Follow up attack rates will be stratified by drug (Takhzyro, Haegarda, and Cinryze) and we will focus on severe attacks only. We will explore the following:

- Adherence to prophylaxis therapy
- Switching behavior between the three prophylaxis drugs
- Attack rates, including attack-free months

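### The ICD-9 and ICD-10 symptom lists for HAE-specific severe attacks are not equivalent, so the case definition changes at the coding switch

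*Protocol*

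**What the plan says.** Annex 2 (Attack severity, Severe) makes an emergency or inpatient event HAE-specific if it meets at least one of four criteria. Two are diagnosis criteria with one entry in each coding system: "Codes often associated with HAE: ICD-9-CM 277.6 or ICD-10-CM D84.1" and "Angioedema diagnosis: ICD-9-CM 995.1 or ICD-10-CM T78.3" (the latter with a wildcard). One does not depend on ICD version: "Administration of on-demand HAE treatment". The fourth is a symptom criterion, "Diagnosis of swelling, abdominal pain, or asphyxiation", with one list per system:

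- "ICD-9-CM 518.81, 518.84, 787.0*, 782.2, 789.0*, 786.02, 786.05, 786.1"
- "ICD-10-CM J96.0*, J96.2*, J96.9*, R06.0*, R06.1, R10.*, R11.*, R22.0*, R22.1, R19.0"

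Section 5.2.1.4 states the intent: "Symptoms and diagnoses codes were cross referenced in a de novo code search to capture both ICD-9 and ICD-10 codes".

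The HAE-specific severe count enters the headline baseline rate in Table 2 (HAE-specific severe plus non-severe), which section 5.4.1.1 pools over the cohort. It is also the only attack rate in Table 3, on which section 5.4.1.3 says: "Follow up attack rates will be stratified by drug (Takhzyro, Haegarda, and Cinryze) and we will focus on severe attacks only". The sensitivity analyses in 5.4.1.4 vary the five-day grouping window and the two on-hand doses. None varies the code list or splits by coding era.

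**The concern.** The two lists should be one definition written in two coding systems. They are unequal on the page: one ICD-9 swelling code faces three ICD-10 entries, and two individual ICD-9 breathing codes face a whole ICD-10 group. With cohort entry from October 2008 to October 2019, the same visit could be an HAE-specific severe attack in one era and not in the other.

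Two results are exposed. The pooled baseline rate would average over two case definitions. It is a candidate input to a cost-effectiveness model that section 4 describes as sensitive to small changes in attack frequency. The follow-up rates in Table 3 stand in adjacent drug columns although the drugs entered the market at different times. If the cost analysis is restricted to 2017–2020, as 5.2.1.5 and 5.2.1.6 allow, it would rest on ICD-10 ascertainment only, while the attack rate would not.

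**Working it through.** The protocol states no figure on this point, so there is none to reproduce.

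**Inputs from the protocol.** The two lists (Annex 2); entry from 10 October 2008, the Cinryze approval, to 3 October 2019, and a 180-day baseline (5.1.1.2); follow-up of at most 365 days and end of data on 31 March 2020 (5.1.1.3); Takhzyro approval on 23 August 2018 (5.1.1.4).

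**Assumptions.** Standard ICD code titles; a coding switch on 1 October 2015, varied by one year either way; Cinryze entry spread evenly over the window, with no early disenrolment. The protocol gives none of these.

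**Step 1: the lists side by side.**

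| Concept | ICD-9 list | ICD-10 list | Matched? |
|---|---|---|---|
| Respiratory failure | 518.81, 518.84 | J96.0*, J96.2*, J96.9* | Entries in both |
| Stridor | 786.1 | R06.1 | Yes |
| Nausea, vomiting | 787.0* | R11.* | Entries in both |
| Abdominal pain | 789.0* | R10.* | Broadly; R10.* also takes tenderness (789.6 not listed) |
| Dyspnoea | 786.02 and 786.05 only | all of R06.0* | No: other dyspnoea in ICD-10 only |
| Head and neck swelling | none (784.2 not listed) | R22.0*, R22.1 | No: ICD-10 only |
| Abdominal swelling | none (789.3 not listed) | R19.0 | No: ICD-10 only |
| Superficial swelling, e.g. limb, trunk | 782.2 | none (R22.2, R22.3, R22.4, R22.9 not listed) | No: ICD-9 only |

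Most gaps make the ICD-9 list narrower; one makes it broader. R19.0 also lacks the wildcard used for other groups. That may be typographical or a loss in text extraction, so it needs confirming and is not counted here as an error.

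**Step 2: time under each system.** The entry window has 4,011 days, of which 2,547 precede 1 October 2015: 2,547 / 4,011 = 63.5%. For an entry day d, follow-up is f(d) = min(365, 31 March 2020 − d), and its ICD-9 part is min(f(d), switch − d), floored at zero. Summing both over all entry days and dividing gives the ICD-9 share of Cinryze time (baseline share computed in the same way from the 180 days before entry):

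| Assumed switch | Baseline | Follow-up |
|---|---|---|
| 1 Oct 2014 | 56.7% | 50.5% |
| 1 Oct 2015 | 65.8% | 59.7% |
| 1 Oct 2016 | 74.9% | 68.9% |

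For Takhzyro, the earliest possible baseline day is 23 August 2018 − 180 days = 24 February 2018. Its ICD-9 share is 0% under all three dates, whatever the entry pattern.

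**Step 3: what the mismatch could do (illustration only).** Let two drugs have the same true severe rate. Let p be the ICD-9 share of Cinryze time, q the share of attacks that qualify only through an unmatched ICD-10 code, and r the share that qualify only through 782.2 at a site without an ICD-10 entry. The measured Cinryze/Takhzyro ratio is

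[(1 − p)(1 − r) + p(1 − q)] / (1 − r).

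- With r = 0 this is 1 − pq. At p = 0.6: 0.97 for q = 5%, 0.94 for 10%, 0.88 for 20%, 0.82 for 30%.
- With q = 0 and r = 10%: 1 + 0.6 × 0.10 / 0.90 = 1.07.
- With q = r the ratio is 1.

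The protocol gives neither q nor r, so neither size nor sign can be fixed.

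**The case against.** The strongest reply is that the mismatch touches little. The HAE and angioedema diagnoses are paired across systems, on-demand treatment qualifies a visit in either era, and abdominal pain, vomiting and respiratory failure have entries on both sides. Only visits identified solely by an unmatched symptom code change. The all-cause severe definition uses no diagnosis list. Rates by drug appear only in Table 3, which is descriptive and which 5.1.1.3 says will not directly feed the model. Section 5.4.1.5 discloses that no validated attack algorithm exists, and the Table 3 footnote already warns that Cinryze initiators were selected differently.

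Most of this stands and limits the point. It does not remove it. Section 5.3.1.2 says drugs given during hospital stays are not recorded, so the treatment route is weak for inpatient events. The all-cause rate is not a row in Table 3, so it offers no check there. Lack of validation is a different problem from a definition that changes with calendar time.

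A reader might infer three stronger things that the documents do not support:

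- *That Cinryze is measured mostly in ICD-9 time.* Initiations by drug and year are not given; the shares above are calendar shares under even entry, and later uptake would lower them.
- *That 782.2 covers swelling at any site, so swelling is simply lost after the switch.* On standard titles it is superficial swelling. Head and neck swelling has its own ICD-9 code, which is unlisted, so the gap runs both ways.
- *That a known part of any drug difference in Table 3 is artefact.* No share of affected visits is available.

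**Conclusion.** The point holds in a limited form. The two symptom lists are not equivalent, despite the stated cross-referencing, and following them as written gives a definition of HAE-specific severe attack that depends on coding era. This affects the HAE-specific severe part of the pooled Table 2 rate and the only attack rate in Table 3. In Table 3, Takhzyro lies wholly in ICD-10 time, and Cinryze follow-up is about 60% ICD-9 time (range 50.5% to 68.9%) under even entry and the assumed switch dates. The Cinryze-versus-Takhzyro contrast does not arise in the primary baseline rate, which is not split by drug.

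The effect on either rate is unknown in size and net direction. The conclusion rests on standard code titles; the unequal treatment of swelling and breathing codes is visible in the lists themselves. No planned sensitivity analysis would reveal the problem.

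**What to change.** 1. Map the lists in both directions. Add to ICD-9 the counterparts for head and neck swelling (784.2), abdominal swelling (789.3) and the dyspnoea within the 786.0 group that R06.0* covers. Add to ICD-10 the remaining R22 sites that correspond to 782.2. Settle abdominal tenderness in the same pass. Do not simply drop 782.2: that would leave ICD-9 with no swelling code while ICD-10 kept its own.
2. Confirm that R19.0 is applied as R19.0*.
3. Report the HAE-specific severe rate separately for ICD-9 and ICD-10 time as a sensitivity analysis.
4. In Table 3, add a Cinryze rate restricted to ICD-10 time beside the full-period rate, not in its place.

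The cost is a code-list edit and one split of data already held. The downside is a small Cinryze group with an imprecise rate in the era-matched row: under even entry and the assumed switch, about 40% of Cinryze follow-up (100% − 59.7%) would remain. This is why the full-period rate should stay, given that the entry window was chosen for sample size.

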5.4.1.4 Sensitivity analyses

We will conduct sensitivity analyses around attack definitions including:

- In our definition of attacks, we considered on-demand therapy administrations by a healthcare professional, ED visits, and inpatient hospitalizations occurring within *five*

days of each other to be considered part of a single attack. We will vary this duration in sensitivity analysis to determine how this impacts attack rates.

- In our definition of non-severe attacks, we assume that patients will have on-demand treatment on hand to treat up to 2 attacks, which is based on treatment guideline recommendations. In sensitivity analysis, we will estimate the number of attacks treated by self-administration without subtracting out two doses to represent drug on-hand.

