Annex 1: HAE drugs

Generic	Brand (Administration)	Acute Attack Dose	Long-Term Prophylaxis Dose	How Supplied
C1 Inhibitor, Human (plasma derived C1 inhibitor [pdC1INH])	Cinryze* (IV)	Adults† 1,000 units once. Additional 1,000 units IV if no improvement 60 minutes after first dose. (not studied in children)	Adults & Children ≥12 years 1,000 units every 3-4 days Max Dose: 2,500 units or 100 units/kg every 3 days Children (6-11 years) 500 units every 3-4 days Max Dose: 1,000 units every 3 days Short-Term Prophylaxis† (before a procedure) 20 units/kg or 1,000 units immediately prior to procedure	Cinryze 500 units Powder Vial Reconstitute with 5mL SWFI Concentration: 100 units/mL
	Haegarda* (SC)		Adults & Children ≥6 years 60 IU/kg twice weekly (every 3-4 days)	Haegarda 2000 IU Powder Vial Reconstitute with 4mL SWFI Concentration: 500 IU/mL Haegarda 3000 IU Powder Vial Reconstitute with 6mL SWFI Concentration: 500 IU/mL
	Berinert* (IV)	Adults & Children ≥6 year 20 IU/kg once		Berinert 500 IU Power Vial Reconstitute with 10mL SWFI Concentration: 50 IU/mL

Generic	Brand (Administration)	Acute Attack Dose	Long-Term Prophylaxis Dose	How Supplied
Lanadelumab	Takhzyro* (SC)		Adults & Children ≥12 years 300mg every 2 weeks. After 6 months, reduce to every 4-week dosing if patient well-controlled.	Takhzyro 300mg/2mL Solution Vial Concentration: 150mg/mL
C1 Esterase Inhibitor, Recombinant (recombinant human C1 inhibitor [rhC1INH])	Ruconest* (IV)	Adults & Children ≥13 years (non-laryngeal attacks) 50 IU/kg/dose Max Dose: 4,200 IU/dose; 8400 IU per 24 hours	Adults & Children ≥13 years† 50 IU/kg/dose once or twice weekly Max Dose: 4,200 IU/dose once or twice weekly Short-Term Prophylaxis† (before a procedure) 50 IU/kg or 1,000 units immediately prior to procedure	Ruconest 2100 IU Powder Vial Reconstitute with 14mL SWFI Concentration: 150 IU/mL
Ecallantide	Kalbitor* (SC)	Adults & Children ≥12 years 30mg once (administered as three injections of 10mg) Max Dose: 60mg in 24 hours		Kalbitor 10mg/mL Vial Solution for Injection (3 vials per package)
Icatibant	Firazyr (SC)	Adults 30mg once. Repeat administrations in 6-hour intervals. Max Dose: 90mg in 24 hours (EU Pediatric Dosing Weight Based)		Firazyr 30mg/3mL Solution Vial Icatibant 30mg/3mL Solution Prefilled Syringe
Berotrastat	Orladeyo* (Oral)		Adults & Children ≥12 years 150 mg once daily. Adjustment: 110mg once daily for hepatic impairment or GI reactions.	Orladeyo 110mg Capsule Orladeyo 150mg Capsule

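### Each dispensed on-demand dose beyond two counts as an attack, so a re-dosed self-treated attack counts more than once, and no listed sensitivity analysis can lower that count

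*Protocol*

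**What the plan says.** Section 5.2.1.4 of the protocol estimates self-treated attacks from dispensed quantity and approved dosage. It starts from the guideline premise that "patients should readily have on-demand therapy to treat two attacks" and concludes that "we will consider any doses dispensed over the two on-hand dosages of on-demand therapy as evidence of an attack". Annex 2 gives the operational rule: "Each dose of an on-demand therapy over two acute attack doses is considered an attack".

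Annex 1 describes acute dosing as follows:
- Firazyr: "30mg once. Repeat administrations in 6-hour intervals. Max Dose: 90mg in 24 hours"
- Kalbitor: 30 mg once, then "Max Dose: 60mg in 24 hours"
- Ruconest: "Max Dose: 4,200 IU/dose; 8400 IU per 24 hours"
- Berinert: a single weight-based dose, with no repeat listed

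For professional administrations, ED visits and hospital stays, section 5.2.1.4 has a merging rule: events "occurring within five days of each other will be considered part of a single attack". Self-administered doses are not in that list.

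Section 5.4.1.4 names two sensitivity analyses on attack definitions. One varies the five-day window. In the other, "we will estimate the number of attacks treated by self-administration without subtracting out two doses to represent drug on-hand".

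**The concern.** The plan accepts that several treatments can belong to one attack, but applies this only to care that generates a dated service claim. Three doses given by a nurse during one attack count once. Three doses self-injected during the same attack count three times, apart from any absorbed by the two-dose deduction.

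The deduction also changes unit. Its rationale is stock for two attacks, but what is subtracted is two doses. The two are equal only if every attack takes exactly one dose.

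The baseline attack rate is a primary outcome, and section 4 says that small changes in attack frequency could substantially change the cost-effectiveness results. Three other Table 2 outputs use the same count: the severity proportions, the self / home nurse / outpatient split, and the share of attacks by on-demand drug. The last would lean toward products with more listed doses per 24 hours.

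**Working it through.** The protocol computes no figure from this rule, so there is none to reproduce. The steps below show scale only.

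**Inputs from the protocol**
- Maximum doses in 24 hours (Annex 1): Firazyr 90/30 = 3; Kalbitor 60/30 = 2; Ruconest 8,400/4,200 = 2; Berinert 1 (no repeat listed). Under the equal 25% drug mix in Table 2 the mean maximum is (3 + 2 + 2 + 1)/4 = 2.0.
- Prior-review comparators (Annex 3, Table 2): 3.39 attacks per month, severe and non-severe together; 64.9% of non-severe attacks self-treated. Neither is an expected result of this study.
- Baseline window: six months.

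**Assumed**
- m, the mean doses per self-treated attack, from 1.0 to 2.0.
- The two doses are deducted once per patient over the six months.
- For the table only, all attacks are non-severe.

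**Formulas.** True attacks in six months: 3.39 × 6 = 20.34. Self-treated: S = 0.649 × 20.34 = 13.20. Professionally treated: H = 7.14.
- Deducted doses truly unused: counted attacks = S·m + H.
- Stock already held, so the deducted doses were used: counted attacks = S·m − 2 + H.

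Rate = counted attacks / 6. Counted self share = self-treated part / total.

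| m | Deducted doses unused: rate, self share | Stock already held: rate, self share |
|---|---|---|
| 1.0 | 3.39 (0%), 64.9% | 3.06 (−10%), 61.1% |
| 1.1 | 3.61 (+6.5%), 67.0% | 3.28 (−3%), 63.7% |
| 1.25 | 3.94 (+16%), 69.8% | 3.61 (+6%), 67.0% |
| 1.5 | 4.49 (+32%), 73.5% | 4.16 (+23%), 71.4% |
| 2.0 | 5.59 (+65%), 78.7% | 5.26 (+55%), 77.4% |

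**Break-even.** With stock already held, the deduction removes 2/6 = 0.33 attacks per month. The two errors cancel at m = 1 + 2/S = 1 + 2/13.20 = 1.15. At one attack per month, S = 6 × 0.649 = 3.89 and break-even is 1 + 2/3.89 = 1.51. There, m = 1.1 gives (3.89 × 1.1 − 2 + 2.11)/6 = 0.73 per month, 27% too low.

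**All-severity rate.** The 64.9% applies to non-severe attacks only. With severe share s and the deducted doses unused, the inflation of the total is (1 − s) × 0.649 × (m − 1). At an assumed s = 20% and m = 1.5 this is 0.8 × 0.649 × 0.5 = 26%, and the severe proportion would read 0.20/1.26 = 16%.

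**Planned sensitivity analyses.** The five-day window does not act on dispensed doses. Dropping the deduction adds up to two attacks per patient. Neither can lower the self-treated count.

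**The case against.** The strongest reply is that one dose per attack follows the base entries in Annex 1: the acute dose is given as once for Firazyr, Kalbitor and Berinert, and the larger figures are 24-hour maxima, not usual use. The protocol reports no re-dosing frequency. The two-dose deduction works the other way and may cancel or outweigh the inflation, especially in patients with few attacks. All of this stands. A reader might infer that the attack rate and the self-treated share are overstated; the documents do not support that as a net statement. Nor do they suggest that the 3.39 in Table 2 came from this rule; Table 2 attributes it to published studies used in the prior review.

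The protocol also says openly that no claims algorithm for attacks is validated, refers to a Model Analysis Plan for criteria on using the estimates, and introduces its sensitivity analyses as an open list. This tempers the consequence: harm to the model input is not shown, and that plan is not at hand. It does not answer the point. The limitations do not mention re-dosing, and criteria for using an estimate, as described, do not change how attacks are counted. Two errors of unknown size cannot be relied on to cancel.

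**Conclusion.** The point holds as a fault in the counting rule, not as a demonstrated net overstatement. Re-dosed self-treated attacks are counted more than once while comparable professionally treated attacks are merged, and no listed analysis tests the direction in which the self-treated count would fall.

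If the deducted doses were unused stock, the non-severe count is inflated by 6.5% at m = 1.1 and by 32% at m = 1.5, and the all-severity rate by less (26% at m = 1.5 with an assumed 20% severe). If stock was already held, the net error is zero near m = 1.15 at 3.39 attacks per month and downward below that. These figures rest on an assumed m and on prior-review comparators. The matter concerns outcome counting only; no dosing rule is judged.

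**What to change.** Add one analysis to section 5.4.1.4 and a matching sentence to Annex 2. For product-specific doses per attack f and dispensed doses D, count attacks as (D − 2f)/f = D/f − 2 with the deduction, and D/f without it. Stock for two attacks is then 2f doses, so the deduction and the count share a unit; f = 1 returns the present rule.

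For the fixed-dose drugs (icatibant and ecallantide, both billed per 1 mg in Annex 2), estimate f in the same data as billed units divided by the acute dose, per merged five-day professionally treated episode outside hospital. For weight-based products use a stated assumed range, because section 5.2.1.1 warns that weight may be limited.

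Report from f = 1 up to the Annex 1 24-hour maximum, with and without the deduction, for the attack rate, severity proportions, treatment-setting split and drug shares. Present this as a range of assumptions, not strict bounds: the present rule is not the highest count, since dropping the deduction exceeds it, and a 24-hour maximum need not be the most used in an attack lasting two to five days.

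The cost is a sentence in Annex 2 and a few extra result rows from data already held. The drawback is that a factor from professionally treated attacks may not hold for home use, which is why the range should be shown.
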